3.3. Tertiary objectives

- To explore the impact of the investigational vaccine on AECOPD.
- To explore the impact of the investigational vaccine on NTHi presence in sputum.
- To explore the impact of the investigational vaccine on health-related quality of life (HRQOL).
- To explore the impact of the investigational vaccine on lung function.
- To explore the impact of the investigational NTHi vaccine on exercise capacity.
- To describe selected biomarkers in stable COPD and during AECOPD.
- To collect blood and sputum samples for assay development, for disease diagnostic purpose, for lung microbiome analysis and/ or for additional evaluation of the immune responses to the investigational vaccine and to other potential pathogens involved in AECOPD.

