4.3. Tertiary endpoints

- Number of cases of NTHi-associated moderate and severe AECOPD, over a period starting 1 month post-Dose 2 and lasting for 1 year, in all subjects.
- Number of cases of NTHi-associated AECOPD (any severity), over a period starting 1 month post-Dose 2 and lasting for 1 year, in all subjects.
- Number of cases of moderate and severe AECOPD (any cause), over a period starting 1 month post-Dose 2 and lasting for 1 year, in all subjects.
- Number of cases of AECOPD (any cause, any severity), over a period starting 1 month post-Dose 2 and lasting for 1 year, in all subjects.
- Time to first AECOPD, in all subjects.
- Assessment of EXACT-PRO score, daily at bedtime throughout the study, in all subjects.
- NTHi presence in sputum, at Screening, Day 90, Day 180, Day 270, Day 360 and Day 450, and from first vaccination to study conclusion for each AECOPD, in all subjects.
- Assessment of CAT score, at Screening, Day 270 and Day 450, and from first vaccination to study conclusion for each AECOPD, in all subjects.
- Assessment of SGRQ-C score, at Screening, Day 270 and Day 450, in all subjects.
- Assessment of mMRC scale, at Screening, Day 270 and Day 450, and from first vaccination to study conclusion for each AECOPD, in all subjects.
- Occurrence of rescue medication use, over a period starting 1 month post-Dose 2 and lasting for 1 year, in all subjects.
- Occurrence of healthcare use for AECOPD, over a period starting 1 month post-Dose 2 and lasting for 1 year, in all subjects.

Statistical Analysis Plan

Study alias & e-track number(s): NTHi-004 (200157)

- Assessment of FEV1% of predicted normal value at Screening, Day 270 and Day 450, in all subjects.
- Assessment of 6MWT score, at Screening and Day 450, in all subjects.
- Occurrence of selected biomarkers in a subset of blood samples, at Day 0 and Day 450, and from first vaccination to study conclusion for each AECOPD, in all subjects.
- Presence of respiratory viral pathogens in sputum (including respiratory syncytial virus, parainfluenza virus, enterovirus/ rhinovirus, metapneumovirus, influenza virus, adenovirus, bocavirus and coronavirus) at Screening, Day 90, Day 180, Day 270, Visit Day 360 and Day 450 and at each AECOPD visit from first vaccination to study conclusion, in all subjects.

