6. STATISTICAL METHODS

6.1. Analysis of demographics

Demographic characteristics (age at the first dose in years, gender and geographical ancestry), cohort description and other characteristics such as smoking/exposure history status, pulmonary function test baseline results and COPD history, history of exacerbation present/past medical history/intercurrent morbidity, and previous vaccination with a pneumococcal vaccine or an influenza vaccine will be summarized by group using descriptive statistics:

- Frequency tables will be generated for categorical variable such as geographical ancestry;
- Mean, median and standard error will be provided for continuous data such as age.

Other characteristics such as height, weight, BMI selected results and several risk factors from the six-minutes-walk test, and distribution of several severity stages using CAT or mMRC or SGRQ-C at enrolment visit will also be summarized.

The number of subjects enrolled into the study as well as the number of subjects excluded from ATP analyses will be tabulated.

The distribution of subjects enrolled among the study sites will be tabulated as a whole and per group.

The numbers of withdrawn subjects will be tabulated according to the reason for withdrawal.

Withdrawal status will be summarised by group using descriptive statistics:

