6.1.5. Analysis of HRQOL, lung capacity and exercise capacity

The analysis will be performed on the TVC. If the percentage of vaccinated subjects excluded from the ATP cohort for efficacy is at least 10%, a second analysis will be performed on the ATP cohort for efficacy to complement the first analysis.

Descriptive statistics (median, mean, range, standard deviation, first and third quartiles) on the **EXACT-PRO**, **CAT**, **SGRQ-C** and **mMRC** scores, on **FEV₁% of predicted normal value** and on the **6MWT** scores will be tabulated by specified visit.

Descriptive summaries **rescue medication and healthcare use for AECOPD** will be provided.

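### HRQOL, FEV1 % predicted and 6MWT get visit tables only: no group difference with CI is specified, and the Screening value is not used as a covariate or change score

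*SAP*

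**What the plan says.** SAP Amendment 1, section 3.3, lists among the tertiary objectives "To explore the impact of the investigational vaccine on lung function" and, as a separate item, "To explore the impact of the investigational NTHi vaccine on exercise capacity", with a matching objective for HRQOL. Section 4.3 fixes the measurement times. One HRQOL entry reads "Assessment of SGRQ-C score, at Screening, Day 270 and Day 450, in all subjects", and CAT and mMRC follow that schedule and are also taken at AECOPD visits. FEV1 % predicted has the same three times. The entry for exercise capacity has one follow-up time only: "Assessment of 6MWT score, at Screening and Day 450, in all subjects".

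The analysis is in SAP 6.1.5, and Protocol 11.11 matches it. Median, mean, range, SD and quartiles are given for EXACT-PRO, CAT, SGRQ-C, mMRC, FEV1 % predicted and 6MWT, and these "scores will be tabulated by specified visit". Neither section names a group difference, a CI, a change from baseline or a model.

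The Screening data do appear elsewhere. SAP 6.1 summarises baseline pulmonary function by group and selected 6MWT results, and adds that the "distribution of several severity stages using CAT or mMRC or SGRQ-C at enrolment visit will also be summarized". These are baseline descriptions and do not enter an effect estimate.

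**The concern.** The objectives speak of impact, and SAP 8.1 and Protocol 11.14.1 list the vaccine's impact on HRQOL, lung function and exercise capacity as part of the final analysis. Section 6.1.5 names no quantity that measures it. The treatment is essentially the one that SAP 6.1.6 gives the biomarkers, whose objective is only to describe.

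The same SAP goes further for other outcomes. Section 6.1.2 gives a GMC ratio with 95% CI, adjusted for the pre-dose concentration, although the immunogenicity objective is only to describe. Section 6.1.3 gives vaccine efficacy with 95% CI for AECOPD, which is also a tertiary objective. So an estimate with an interval fits this descriptive study.

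At stake is how the Day 270 and Day 450 tables can be read. A reader who compares two means by eye has no interval and no allowance for a difference already present at Screening.

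**Working it through.** **The plan's own figure.** The only sample-size basis is the chance of seeing at least one AE among 70 subjects (Protocol 11.4), which is 1 − (1 − p)^70.
- p = 1%: 1 − 0.99^70 = 0.505 (stated: more than 50%).
- p = 5%: 1 − 0.95^70 = 0.972 (stated: more than 97%).

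Both reproduce. No precision figure is given for HRQOL, FEV1 or 6MWT, so there is none to check for these outcomes.

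**Inputs.**
- n = 70 per arm, allocated 1:1 (Protocol 5.1 and 6.2.2.2.1).
- Two-sided 95% CI (SAP 7.1.3).
- Correlation ρ between Screening and follow-up: not in the documents; 0.5, 0.7 and 0.8 assumed.
- Equal SD at both times: assumed. Results are in SD units, using the normal quantile 1.96.

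**Formulas for the 95% CI half-width of the group difference.**
- Follow-up value only: 1.96 × √(2/70) = 0.331.
- Change from Screening: 0.331 × √(2(1 − ρ)).
- ANCOVA on the Screening value: 0.331 × √(1 − ρ²).

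| ρ (assumed) | Follow-up only | Change score | ANCOVA | ANCOVA vs follow-up only | ANCOVA vs change score |
|---|---|---|---|---|---|
| 0.5 | 0.331 | 0.331 | 0.287 | 13% narrower | 13% narrower |
| 0.7 | 0.331 | 0.257 | 0.237 | 29% narrower | 8% narrower |
| 0.8 | 0.331 | 0.210 | 0.199 | 40% narrower | 5% narrower |

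The last two columns are 1 − √(1 − ρ²) and 1 − √((1 + ρ)/2).

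**With dropout.** If 20% are lost (assumed), 56 per arm remain. Follow-up only gives 1.96 × √(2/56) = 0.370 SD. Change scores give 0.370, 0.287 and 0.234 SD, and ANCOVA gives 0.321, 0.265 and 0.222 SD. The pattern is the same.

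**Chance imbalance at Screening.** Ignoring any indirect balance from minimisation, a baseline gap of 0.2 SD corresponds to z = 0.2/√(2/70) = 1.18. The chance of a larger gap in either direction is about 24% for any one scale.

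**The case against.** The strongest reply is that this is a choice suited to the tier. The endpoints are tertiary, the sample size rests on AE detection, and Protocol 11.13 and 11.14.2 declare the comparisons and analyses descriptive. That stands in part: no test, decision or power claim depends on section 6.1.5, and the gap is a missing estimate, not a missing test. It does not explain why AECOPD, in the same tier, gets an estimate with a CI.

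Three stronger readings are tempting, and the documents do not support them.

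- *Visit means cannot estimate a vaccine effect.* Allocation is randomised 1:1, so the difference in follow-up means is unbiased, apart from dropout, which an ANCOVA on completers would share. If the tables are by group, a reader could derive a difference and its CI from the means, SDs and Ns. Section 6.1.5 does not say by group, but SAP section 2 sets group labels for tables, and table layout is left to an annex that is not among the documents.
- *The baselines are not used.* Screening is one of the assessment visits, and SAP 6.1 summarises baseline values. What is absent is their use as a covariate or change score.
- *Imbalance is unguarded.* Minimisation uses age group, AECOPD history and GOLD grade. GOLD grade is a cut of FEV1 % predicted (Protocol Table 1), so gross FEV1 imbalance is already limited. CAT, SGRQ-C and 6MWT are not balanced directly, but a gap would show in the Screening row.

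A fair point on any remedy is that it adds seven intervals (three scales at two visits, plus 6MWT). If they were independent and there were no effects, the chance that at least one excludes zero is 1 − 0.95^7, about 30%.

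**Conclusion.** The point holds as a gap between objective and analysis. Three objectives about impact have no specified between-group quantity, and Screening values already collected are not used to sharpen one.

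The size depends on an assumed correlation and on the comparator. Against follow-up values alone, ANCOVA narrows the CI by 13% to 40% for ρ from 0.5 to 0.8. A reader might infer that this is worth up to 2.8 times the sample (70/(1 − 0.8²) = 194 per arm). That figure applies only at ρ = 0.8 and only against a follow-up-only comparison. Against a simple change score from the same data, the gain is 13%, 8% and 5%. The larger benefit is having a stated difference with an interval at all.

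This is a cheap improvement to exploratory analyses. It does not touch the primary safety objective.

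**What to change.** In SAP 6.1.5, keep the visit tables and state that they are shown by group. Add one paragraph:

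- For CAT, SGRQ-C and FEV1 % predicted at Day 270 and Day 450, and for 6MWT at Day 450, fit an ANCOVA of the follow-up value on group, Screening value and the three minimisation factors (age group, previous-year moderate/severe AECOPD count, GOLD grade).
- Report the adjusted mean difference, vaccine minus control, with its two-sided 95% CI. Label it exploratory, with the caution that SAP 6.1.2 already gives for GMCs about no adjustment for multiplicity.
- State the number of subjects with data at each visit, since withdrawals are not replaced (Protocol 10.2).
- Use scheduled visits only. CAT at AECOPD visits depends on a post-randomisation event and should stay separate.
- Leave mMRC (ordinal) and EXACT-PRO (daily, so it would need a defined window) as descriptive summaries by group.

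The cost is one SAP paragraph and a few exploratory tables, with no new data. The downside is seven more unadjusted intervals, which the label and caution should cover.

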6.1.6. Analysis of selected biomarkers

The analysis will be performed on the ATP cohort for efficacy. If the percentage of vaccinated subjects excluded from the ATP cohort for efficacy is at least 10%, a second analysis will be performed on the TVC to complement the first analysis.

For each type of timepoint (Pre, Exacerbation visit, Day 450) during which blood samples are collected for analysis of biomarkers, descriptive statistics will be tabulated for each selected biomarker.

Statistical Analysis Plan

Study alias & e-track number(s): NTHi-004 (200157)

6.1.7. Analysis of sputum

The analysis will be performed:

- By aggregating all laboratory sites where the sputum was tested
- By laboratory site in order to evaluate if differences exist in the way of testing sputum
- By country (aggregating all laboratory sites by country).

6.1.7.1. Sputum sample collection and quality

The proportion of subjects (at each stable and exacerbation visit) who provided a sputum sample will be computed; overall and by the sample method (spontaneous or induced).

The proportion of sputum of good quality will be computed.

The proportion of subjects with induced sputum will be tabulated by COPD status at enrolment and by severity of the AECOPD.

The distribution of the time (in days) between the start of exacerbation and the day of the sputum sample collection will be presented.

6.1.7.2. Sputum bacterial/viral results from culture or from PCR

The distribution of the proportion of sputum samples positive given the number of days between start of exacerbation and sample collection will be presented.

The proportion of sputum samples obtained at each - stable and exacerbation - visit and positive for specific bacterial/viral pathogens (overall and by bacterial culture, by bacterial PCR, or by viral species) will be computed. The average infection rate by type of visit will also be calculated.

The bacterial presence in culture versus the bacterial presence in PCR detected in sputum will be tabulated.

The viral infections versus the bacterial presence in PCR detected in sputum will be tabulated.

The incidence of exacerbations and of exacerbations containing Hi, Mcat, Sp, and all bacterial and/or virus that are planned to be tested by the laboratory will be presented.

Statistical Analysis Plan

Study alias & e-track number(s): NTHi-004 (200157)

For specific bacterial pathogens, the quantitative assessment of PCR results will be provided overall, for sputum samples positive in culture, or negative in culture of the specific pathogen.

The same analyses should be performed by taking into account only the sputum that has a good quality.

6.1.7.3. Impact of previous antibiotic administration on sputum bacterial results

The impact of antibiotic administration before sputum collection on the bactericidal culture or PCR results will be evaluated, for stable (scheduled) visits, exacerbation visits, or any visit.

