5.2. Inclusion criteria for enrolment

Deviations from inclusion criteria are not allowed because they can potentially jeopardise the scientific integrity of the study, regulatory acceptability or subject safety. Therefore, adherence to the criteria as specified in the protocol is essential.

All subjects must satisfy ALL the following criteria at study entry:

- Subjects who, in the opinion of the investigator, can and will comply with the requirements of the protocol (*e.g.* electronic Diary Card completion, number of blood draws, sputum sampling, pre- and post-bronchodilator spirometry, return for follow-up visits).
- A male or female between, and including, 40 and 80 years of age at the time of the first vaccination.
- Written informed consent obtained from the subject.

- Confirmed diagnosis of COPD (based on post-bronchodilator spirometry) with forced expiratory volume in 1 second (FEV₁) over forced vital capacity (FVC) ratio (FEV₁/FVC) < 0.7, **AND** FEV₁ < 80% and ≥ 30% predicted (GOLD 2 and 3).

- Current or former smoker with a cigarette smoking history of ≥ 10 pack-years.
Refer to the [glossary of terms](#) for the definitions of pack-years and of current and former smoker.

- Stable COPD patient* with documented history (e.g. medical record verification) of at least 1 moderate or severe AECOPD within the 12 months before Screening.

* Patient for whom the last episode of AECOPD is resolved for at least 30 days at the time of Screening.

Refer to the Study Procedures Manual (SPM) for details on what is accepted as documented history of AECOPD. Refer to [Table 2](#) for the definitions of moderate and severe AECOPD.

- Regular sputum producer.
- Capable to comply with the daily electronic Diary Card completion throughout the study period, according to investigator's judgement at Visit 1.

Refer to the SPM for recommendations on what is considered adequate compliance by Visit 1.

- Female subjects of non-childbearing potential may be enrolled in the study.
 - Non-childbearing potential is defined as current tubal ligation, hysterectomy, ovariectomy or post-menopause.
Refer to the [glossary of terms](#) for the definition of menopause.
- Female subjects of childbearing potential may be enrolled in the study, if the subject:
 - has practiced adequate contraception for 30 days prior to vaccination, and
 - has a negative pregnancy test on the day of vaccination, and

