6.5.2. List of study procedures during AECOPD-driven study visits and phone contacts

In addition to the scheduled study visits, *ad-hoc* AECOPD-driven study contacts will take place for each AECOPD occurring from first vaccination up to study conclusion. The procedures to be performed during these contacts are listed in [Table 8](#).

In case of AECOPD occurring before Visit 1, subjects should be treated outside the study according to standard practice. These subjects can only continue in the study if the entire Screening Visit is repeated after they are stable for at least 30 days.

Table 8 List of study procedures during AECOPD-driven study visits and phone contacts

Type of contact	AECOPD visit	End of AECOPD contact(s) (phone call[s] and/ or visit[s])
Timepoint	within 96 hours of onset symptoms	at least every 2 weeks as of AECOPD visit until AECOPD has resolved ^(a)
Sampling timepoint	AECOPD	
Record date of visit	●	
Physical examination	○	○ ^(b)
Chest X-ray ^(c)	●	
Confirm AECOPD and record its start date	●	
Blood sampling:		
For biomarkers (~12.8 mL)	●	
For haematology assessment (~2 mL)	●	
Sputum sampling ^(d)	●	
HRQOL questionnaires:		
CAT	x	
mMRC	x	
Record healthcare use for AECOPD (medical record review)	○	●
Record AEs	●	●
Report SAEs	●	●
Report pregnancies ^(e)	●	●
Record concomitant medications/products and vaccinations	●	● ^(b)
Record intercurrent medical conditions requiring medical attention	●	●
Record AECOPD severity	○	●
Record AECOPD end date		●

● is used to indicate a study procedure that requires documentation in the individual eCRF.

○ is used to indicate a study procedure that does not require documentation in the individual eCRF.

x is used to indicate a study procedure that does not require documentation in the individual eCRF as the data will be directly transferred from the provider to GSK.

^a End of AECOPD phone calls/ visits should be scheduled at least every 2 weeks, until the AECOPD has resolved.

Only the contact during which the end date of the AECOPD can be determined will be recorded in the eCRF as the end of the AECOPD contact. All intermediate contacts should be recorded on source documentation.

^b Only applicable if the contact is a visit (not for phone calls).

^c Only if clinically indicated to exclude another cause of worsening of symptoms (e.g. pneumonia).

^d Only if, in the opinion of the investigator, it is safe for the subject.

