6.5.3. Concurrence of AECOPD-driven study visits and scheduled study visits

If an AECOPD occurs at the time of a scheduled study visit, it should be handled and recorded as an AECOPD visit, with all relevant study procedures performed and, if possible, the scheduled visit should be re-scheduled to a later date within the time window specified in the protocol. In consultation with GSK, only Visit 8 (Day 270) and Visit 10 (Day 450) may exceptionally be conducted outside of the allowed interval if necessary.

If an end of AECOPD contact occurs around the same time of a scheduled study visit, they can be combined into a single visit with the study procedures relevant to both visit types performed. In this case, both visit types will need to be recorded in the eCRF separately.

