6.6.4. Check subject's COPD status

Record the subject's COPD status (stable/ recovered or not recovered) in the eCRF.

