6.1.7.5. Impact of previous occurrence of Hi bacterial pathogen in sputum on AECOPDs

The impact of the occurrence or presence of respiratory pathogenic bacteria detected in sputum at the exacerbation visit given the presence of the bacteria at previous visits on the number of exacerbations will also be studied. In order to do this, 2 types of AECOPDs will be distinguished:

- AECOPDs in which Hi is present and was not present any previous visit
- AECOPDs in which Hi is present and was not present in the previous stable visit;

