- For summaries of the number of AECOPD occurring during the 1 year follow-up period starting 1 month post-Dose 2, an exacerbation rate will be calculated for each subject. The number of exacerbations during the 1-year follow-up period will be imputed for subjects withdrawing from the study to provide an estimate of the number of exacerbations over the follow-up period. This calculation will only be performed for purposes of reporting summary statistics for the rate of exacerbations during the 1 year follow-up period since the modelling of exacerbations takes into account the number of exacerbations and the time of follow-up for each subject. The calculation of exacerbation rate will be based on follow-up period intervals to avoid obtaining high imputed rates if a subject withdrew very early in the follow-up period after experiencing an exacerbation. Since treatment courses for moderate/severe exacerbations are $\leq 2 - 4$ weeks when appropriate, calculated numbers of exacerbations for subjects withdrawing from the study will be based on 4-week intervals of the follow-up period. For subjects followed for less than 1 year, the number of exacerbations during the 1-year follow-up period will be calculated by multiplying the number of exacerbations experienced by the subject by 13 and dividing by the number of 4-week periods the subject was followed up:

Statistical Analysis Plan

Study alias & e-track number(s): NTHi-004 (200157)

Number of exacerbations per year = Number of exacerbations * 13 /Number of 4-week treatment period intervals

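### SAP section 6.1.7 treats scheduled sputum visits as stable visits, although a post-vaccination scheduled visit can fall inside an unresolved AECOPD

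*SAP*

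**What the plan says.** **The label.** SAP Amendment 1, 6.1.7.1 and 6.1.7.2, reports sputum collection and pathogen results by stable and exacerbation visit. In 6.1.7.3 and 6.1.7.4, the effects of prior antibiotics and of sputum induction "will be evaluated, for stable (scheduled) visits, exacerbation visits, or any visit", so the two words are made equivalent. Section 6.1.7.5 then defines two AECOPD classes. One looks back to any previous visit; the other is "AECOPDs in which Hi is present and was not present in the previous stable visit". The SAP gives no definition of a stable visit.

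**The visit rules.** Protocol Table 9, footnote 5, keeps scheduled visits at least 7 days away from an AECOPD visit. Under Protocol 6.5.3, an AECOPD at the time of a scheduled visit is handled as an AECOPD visit and, if possible, "the scheduled visit should be re-scheduled to a later date within the time window specified in the protocol". The same section adds: "If an end of AECOPD contact occurs around the same time of a scheduled study visit, they can be combined into a single visit". Follow-up may be slower than the 7-day gap (Table 8, footnote a): "End of AECOPD phone calls/ visits should be scheduled at least every 2 weeks, until the AECOPD has resolved".

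**What is recorded.** Protocol 6.6.4 says: "Record the subject's COPD status (stable/ recovered or not recovered) in the eCRF". Table 7 schedules this at Visits 1 to 10. Onset and end dates of each confirmed AECOPD are also recorded (Protocol 4.1.1). SAP 6.1.4 uses the status only to tabulate the percentage of visits that were recovered/stable.

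**The concern.** The 7-day gap runs from the AECOPD visit, not from resolution, so a scheduled visit can meet every protocol rule while the subject has not recovered. The SAP still places its sputum in the stable class.

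Three outputs are affected:

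- **Carriage at stable visits** (6.1.7.1, 6.1.7.2) mixes stable and exacerbation samples.
- **The 6.1.7.5 class based on the previous stable visit** can be wrong in both directions. Hi cultured during an unresolved episode counts as prior stable carriage, so a later Hi-positive AECOPD is not counted as new. A culture suppressed by antibiotics can be falsely negative, so a later Hi-positive AECOPD looks new when it may not be.
- **Biomarkers.** The objective is to describe them in stable COPD and during AECOPD. Day 450 is the only scheduled post-vaccination sample, and SAP 6.1.6 summarises it without regard to recovery.

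If the vaccine changes how often AECOPD occur or how long they last, the share of misclassified visits will differ between groups.

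**Working it through.** **1. The rules side by side**

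| Setting | Separation required | Counted from |
|---|---|---|
| Screening (Protocol 5.2) | at least 30 days | resolution |
| Vaccination, moderate/severe AECOPD (Protocol 7.5) | at least 7 days | resolution |
| Any scheduled visit (Table 9, footnote 5) | at least 7 days | the AECOPD visit |

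The Screening rule reads: "Patient for whom the last episode of AECOPD is resolved for at least 30 days at the time of Screening". If an AECOPD occurs before Visit 1, the whole Screening Visit is repeated after at least 30 stable days. Systemic antibiotics in the 30 days before Screening are an exclusion (Protocol 5.3). Screening sputum is thus protected on both counts. Scheduled sputum at Visits 6 to 10 has neither protection.

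**2. Can an episode outlast the gap?** The AECOPD visit takes place within 96 hours (4 days) of onset, so the earliest compliant scheduled visit is 7 to 11 days after onset. SAP 7.1.3 has a sentence opening "Since treatment courses for moderate/severe exacerbations are" that goes on to give 2 to 4 weeks as the upper limit. An episode lasting longer than 7 to 11 days is therefore plausible on the plan's own terms.

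**3. Size.** The plan states no figure for this, so there is none to reproduce. Rate and duration are assumptions.

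Inputs:
- Rate r = 1 or 2 AECOPD per subject-year (assumed, Poisson).
- Duration T with mean m = 7, 14 or 21 days (assumed, gamma with shape 2).
- AECOPD visit 0 to 4 days after onset, midpoint 2 (from the 96-hour rule).
- A visit due before the AECOPD visit + 7 days is moved to that day. The cut-off is therefore c = 2 + 7 = 9 days after onset.

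A scheduled visit falls in an unresolved episode if it was due during an episode longer than c. Ignoring overlapping episodes:

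share = (r / 365) × E[T; T > c] = (r / 365) × m × S

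Here S = exp(−x)(1 + x + x²/2) and x = 2c/m.

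| m (days) | x | S | m × S (days) | share, r = 1 | share, r = 2 |
|---|---|---|---|---|---|
| 7 | 2.571 | 0.526 | 3.68 | 1.0% | 2.0% |
| 14 | 1.286 | 0.860 | 12.05 | 3.3% | 6.6% |
| 21 | 0.857 | 0.944 | 19.82 | 5.4% | 10.9% |

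A simulation of the same rules, with overlaps allowed, gives 1.0%, 3.2% and 5.3% at r = 1, and 2.0%, 6.5% and 10.4% at r = 2. The two methods agree; overlaps explain most of the small difference at the top.

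Planned scheduled sputum samples after vaccination: 140 subjects × 5 visits (Visits 6 to 10) = 700. Applying the simulated shares gives about 7, 23 and 37 samples at r = 1, and about 14, 45 and 72 at r = 2.

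**4. What does not depend on the label.** SAP 7.1.4 defines an NTHi-associated AECOPD from the AECOPD sample alone, so the incidence and vaccine efficacy analyses in 6.1.3 do not use stable visits. The Hi incidence model in 6.1.3 refers to the previous visit. The other 6.1.7.5 class refers to any previous visit.

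**The case against.** The strongest reply has four parts.

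**The SAP does not assume that every visit is stable.** It tabulates recovered/stable status in 6.1.4. That is true. It also shows that the plan expects some unrecovered scheduled visits, yet 6.1.7 never uses the status to classify a sample.

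**The protocol already moves clashing visits.** It does, and Protocol 6.5.3 even lets Visits 8 and 10 leave the window. (Table 9, footnote 5, names only Visit 10; the two passages must be reconciled.) But the move is made if possible and stops at 7 days, not at resolution. The rule on combined visits is weak evidence for the concern, because only the contact at which the end date can be determined is recorded as the end-of-AECOPD contact.

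**Section 6.1.7.3 already studies antibiotics.** It describes their effect on sputum results. It does not change the look-back in 6.1.7.5. Conversely, a recovery flag alone would not remove a visit where symptoms have resolved but antibiotics continue or have just ended. That stands, and it is why the fix includes a separate antibiotic flag.

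**The stakes are low.** The outputs are descriptive and tertiary, and Protocol 11.13 asks for caution in reading comparisons. The SAP's annex of tables, figures and listings, which is not among the documents, may also hold table-level definitions. This limits the weight of the point but does not remove the stated equivalence.

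A reader might go further and infer that FEV1, 6MWT, CAT, SGRQ-C and mMRC are also mislabelled as stable. The documents do not support that. SAP 6.1.5 tabulates them by visit and never calls them stable. Describing randomised groups as observed at Day 270 and Day 450 is legitimate, and restricting to recovered subjects would condition on a post-randomisation state.

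**Conclusion.** The point holds for sputum and, in a lesser form, for Day 450 biomarkers. As written, SAP 6.1.7 places some samples from unresolved AECOPD in the stable class, and one of the two classes in 6.1.7.5 inherits the error. Under the assumed 1 to 2 AECOPD per year and mean durations of 7 to 21 days, this is about 1% to 10% of scheduled visits. With a 7-day mean, it is only 1% to 2%. The range rests wholly on assumed rate and duration, and on visits being moved whenever the 7-day rule requires.

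Two larger claims should not be drawn from this. It is not every scheduled visit, since Screening and Visit 1 are protected. Nor should Screening's 30-day rule be applied to follow-up visits to obtain a bigger share. With 4 to 20 unresolved days beyond day 10, that would give 1 × (4 + 30)/365 = 9.3% to 2 × (20 + 30)/365 = 27%. But the 30 days are an enrolment criterion; the protocol does not impose them on follow-up visits, and the definition proposed below does not use them.

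The correction is worth making because it is cheap and replaces a stated equivalence that the visit rules contradict. It does not bear on the primary, secondary or vaccine efficacy analyses.

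**What to change.** In SAP 6.1.7:

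1. Define a stable visit as a scheduled visit with eCRF COPD status stable/recovered and a date outside every recorded AECOPD onset-to-end interval.
2. Report scheduled visits that fail either condition as a separate class.
3. Apply this in 6.1.7.1 to 6.1.7.5. State that the look-back in 6.1.7.5 goes to the most recent visit that meets the definition.
4. In 6.1.7.5, flag look-back samples taken under or soon after systemic antibiotics, with the number of days stated in advance, and show the classification with and without them.

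In SAP 6.1.6, show Day 450 biomarkers by the same recorded status beside the all-subject table. Leave the FEV1, 6MWT and HRQOL by-visit tables as planned.

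The cost is SAP wording plus two flags derived from COPD status, AECOPD dates and concomitant medication, all already in the eCRF. No visit, sample or protocol procedure changes. The downside is a slightly smaller stable class that is selected after randomisation. The all-scheduled-visit tables should therefore be kept beside it.
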